**Table 8. Criteria for Potentially Clinically Important Chemistry Values**

Chemistry Variables	Units	Definition of Potentially Clinically Important Current (Version 4) NCI CTCAE Grade 3 or Greater	
		Very Low	Very High
TBL	mcmol/L		> 3.0 × ULN
SGOT/AST	U/L		> 5.0 × ULN
SGPT/ALT	U/L		> 5.0 × ULN
Albumin	g/L	< 20	
Glucose	mmol/L	< 2.2	> 13.9
Triglycerides	mmol/L		> 5.7
Creatinine	mcmol/L		> 3.0 × ULN
Sodium	mmol/L	< 130	> 155
Potassium	mmol/L	< 3.0	> 6.0
Calcium	mmol/L	< 1.75	> 3.1
CPK	U/L		> 5.0 × ULN
Total Cholesterol	mmol/L		> 10.34
GGT			> 5.0 × ULN
ALP			> 5.0 × ULN

**Table 9. Criteria for Potentially Clinically Important Hematology Values**

Hematology Variables	Units	Definition of Potentially Clinically Important Current (Version 4) Grade 3 or Greater	
		Very Low	
Hemoglobin	g/dL	< 8.0	
Platelets count	10  /L	< 50.0	
WBC count	10  /L	< 2.0	
Neutrophils	10  /L	< 1.0	
Lymphocytes	10  /L	< 0.5	

A separate listing will be provided that presents all of the subjects and values that are NCI CTCAE toxicity grade 3 or above. For each of these subjects, the whole course of the respective parameter will be listed. The NCI CTCAE grading is shown in [Table 10](#) below:

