### 11.3.2 Statistical Methods

#### Analysis of Continuous Laboratory Parameters

Analyses of laboratory data will be presented based on the National Cancer Institute Common Toxicity Criteria for Adverse Event (NCI CTCAE) scale. Change from Baseline to each scheduled visit and to the final value in continuous laboratory parameters will be summarized with the mean, standard deviation and median. The Baseline and visit/final value means will also be presented for subjects who have both the Baseline and

visit/final values (see Section 6.0 for the definition of Baseline and final values). If there are multiple post-baseline measurements on the same day, the average value will be used.

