### **Potentially Clinically Important Laboratory Values**

Frequencies and percentages of subjects with post Baseline lab values meeting the following criteria will be summarized.

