**Table 10. NCI CTCAE Grading**

Test	Grade 1	Grade 2	Grade 3	Grade 4
SGPT/ALT increased	$> \text{ULN} - 3.0 \times \text{ULN}$	$> 3.0 - 5.0 \times \text{ULN}$	$> 5.0 - 20.0 \times \text{ULN}$	$> 20.0 \times \text{ULN}$
SGOT/AST increased	$> \text{ULN} - 3.0 \times \text{ULN}$	$> 3.0 - 5.0 \times \text{ULN}$	$> 5.0 - 20.0 \times \text{ULN}$	$> 20.0 \times \text{ULN}$
GGT increased	$> \text{ULN} - 2.5 \times \text{ULN}$	$> 2.5 - 5.0 \times \text{ULN}$	$> 5.0 - 20.0 \times \text{ULN}$	$> 20.0 \times \text{ULN}$
ALP increased	$> \text{ULN} - 3.0 \times \text{ULN}$	$> 3.0 - 5.0 \times \text{ULN}$	$> 5.0 - 20.0 \times \text{ULN}$	$> 20.0 \times \text{ULN}$
TBL increased	$> \text{ULN} - 1.5 \times \text{ULN}$	$> 1.5 - 3.0 \times \text{ULN}$	$> 3.0 - 10.0 \times \text{ULN}$	$> 10.0 \times \text{ULN}$
Creatinine increased	$> \text{ULN} - 1.5 \times \text{ULN}$	$> 1.5 - 3.0 \times \text{ULN}$	$> 3.0 - 6.0 \times \text{ULN}$	$> 6.0 \times \text{ULN}$
CPK increased	$> \text{ULN} - 2.5 \times \text{ULN}$	$> 2.5 - 5.0 \times \text{ULN}$	$> 5.0 - 10.0 \times \text{ULN}$	$> 10.0 \times \text{ULN}$
Hemoglobin decreased	$< \text{LLN} - 100.0 \text{ g/L}$	$< 100.0 - 80.0 \text{ g/L}$	$< 80.0 - 65.0 \text{ g/L}$	N/A
Neutrophil count decreased	$< \text{LLN} - 1.5 \times 10^9/\text{L}$	$< 1.5 - 1.0 \times 10^9/\text{L}$	$< 1.0 - 0.5 \times 10^9/\text{L}$	$< 0.5 \times 10^9/\text{L}$
WBC decreased	$< \text{LLN} - 3.0 \times 10^9/\text{L}$	$< 3.0 - 2.0 \times 10^9/\text{L}$	$< 2.0 - 1.0 \times 10^9/\text{L}$	$< 1.0 \times 10^9/\text{L}$
Lymphocyte count decreased	$< \text{LLN} - 0.8 \times 10^9/\text{L}$	$< 0.8 - 0.5 \times 10^9/\text{L}$	$< 0.5 - 0.2 \times 10^9/\text{L}$	$< 0.2 \times 10^9/\text{L}$

If there are multiple post-baseline measurements on the same day, the worst value will be used.

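### SAP Table 10, the grading cited for the grade 3+ laboratory listing, leaves haemoglobin below 65 g/L ungraded and has no row for six post-baseline parameters given grade 3 limits in Tables 8 and 9

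*SAP*

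**What the plan says.** SAP Section 11.3.2 opens with a general rule: "Analyses of laboratory data will be presented based on the National Cancer Institute Common Toxicity Criteria for Adverse Event (NCI CTCAE) scale". Three elements then bear on severe laboratory values.

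- **Frequency summary.** "Frequencies and percentages of subjects with post Baseline lab values meeting the following criteria will be summarized". The criteria are the limits in Table 8 (chemistry), headed "Definition of Potentially Clinically Important Current (Version 4) NCI CTCAE Grade 3 or Greater", and Table 9 (haematology), headed "Definition of Potentially Clinically Important Current (Version 4) Grade 3 or Greater".
- **Targeted listing.** After Table 9 the SAP says: "A separate listing will be provided that presents all of the subjects and values that are NCI CTCAE toxicity grade 3 or above". For each such subject the full course of the parameter is to be shown.
- **Grading.** The next sentence begins "The NCI CTCAE grading is shown in" and refers to Table 10, which sets out grades 1 to 4 test by test.

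For haemoglobin, Table 9 gives a single limit of below 8.0 g/dL with no floor. In Table 10 the row "Hemoglobin decreased" gives grade 3 as below 80.0 down to 65.0 g/L, and grade 4 as N/A. Table 9 also has a row "Platelets count" with a limit of below 50.0 × 10⁹/L; Table 10 has no platelet row.

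**The concern.** The summary and the listing are meant to describe the same thing, namely subjects with grade 3 or worse values. A reader of the report will expect everyone counted in the summary to be traceable in the listing. That holds only if both use the same definition, and the SAP gives two that do not cover the same ground.

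Haemoglobin is the sharper problem because the two tables assign different status to the same value. A result below 65 g/L is grade 3 or greater by Table 9 and has no grade by Table 10, so the most extreme results are the ones that lose their grade. For the parameters with no row, a strict use of Table 10 gives the programmer nothing to grade with. What is at stake is one targeted safety listing. Its value is that it shows the course of the parameter over time for each flagged subject, which a count cannot do.

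**Working it through.** No sample size, power or test statistic is involved. The check compares the three tables.

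**Parameters with a grade 3 or greater limit**

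- Table 8 has 14: total bilirubin, AST, ALT, albumin, glucose, triglycerides, creatinine, sodium, potassium, calcium, CPK, total cholesterol, GGT, ALP.
- Table 9 has 5: haemoglobin, platelets, WBC, neutrophils, lymphocytes.
- Total: 14 + 5 = 19.

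**Rows in Table 10**

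- There are 11: ALT, AST, GGT, ALP, total bilirubin, creatinine, CPK, haemoglobin, neutrophils, WBC, lymphocytes. All are among the 19.
- No row: 19 − 11 = 8, namely albumin, glucose, triglycerides, sodium, potassium, calcium, total cholesterol and platelets.

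**Restriction to values the summary can count**

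- The frequency summary uses post-baseline values only. SAP Table 7, footnote a, restricts triglycerides and total cholesterol to Screening, so they have no scheduled value that could be counted and then left unlisted.
- Parameters without a row that matter in practice: 8 − 2 = 6, out of 19 − 2 = 17, or 6/17 = 35%.
- These six carry 10 separate limits: albumin 1, glucose 2, sodium 2, potassium 2, calcium 2, platelets 1.

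**Agreement on the 11 shared parameters**

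The entry point to grade 3 is the same in Table 10 as in Tables 8 and 9: 5 × ULN for ALT, AST, GGT, ALP and CPK; 3 × ULN for bilirubin and creatinine; 80 g/L for haemoglobin; and 1.0, 2.0 and 0.5 × 10⁹/L for neutrophils, WBC and lymphocytes. Ten of the 11 rows end in an open-ended grade 4. Haemoglobin is the exception.

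**Haemoglobin (8.0 g/dL × 10 = 80 g/L)**

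| Value (g/L) | Meets Table 9 limit (< 80) | Grade 3 or above in Table 10 (65 to < 80) |
|---|---|---|
| 85 | no | no |
| 79 | yes | yes |
| 70 | yes | yes |
| 65 | yes | yes |
| 64 | yes | no grade |
| 50 | yes | no grade |

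The tables agree down to 65 g/L and diverge below it.

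**Which table governs the listing**

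The reference to Table 10 follows directly on the listing rule, and Table 10 is the only place where the SAP sets out the scale grade by grade. Elsewhere the SAP names the criteria for a listing explicitly: the liver listing in Section 11.3.2 has its own four criteria, and the vital-sign listing in Section 11.4.2 uses the same criteria as its counts. The grade 3+ laboratory listing has no such statement tying it to Tables 8 and 9.

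**The case against.** The strongest reply is that Table 10 does not define the listing. The rule asks for all grade 3 or above values, and Tables 8 and 9, placed just before it, already label their limits that way for all 19 parameters. On that reading a glucose above 13.9 mmol/L, a platelet count below 50 × 10⁹/L or a haemoglobin of 60 g/L is listed, and Table 10 only illustrates the grades for selected tests. This reading is open to a programmer, so it cannot be said that the listing will omit these subjects. But the SAP does not choose it, the sentence after the rule points to Table 10, and the haemoglobin conflict remains under either reading.

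Four further points limit the size of the problem, and all stand.

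- A missing row is not a numerical contradiction. A reader might infer that the tables disagree generally, but every shared grade 3 entry point agrees. Only haemoglobin below 65 g/L is in conflict.
- A reader might infer that safety reporting as a whole is incomplete. It is not. SAP Section 11.3 plans listings of laboratory values and of subjects with significant abnormalities, and Section 11.3.2 gives shift tables to minimum, maximum and final value for each haematology and chemistry parameter, besides the counts.
- Extreme haemoglobin and platelet values should be rare: Protocol Section 5.2.2, criterion 14, excludes anyone with a blood-count parameter outside normal range at Screening, and about 110 subjects are planned. A subject who also has a haemoglobin of 65 to below 80 g/L at some point would be listed anyway.
- SAP Section 17.0 leaves the list of tables, figures and listings to a separate document, which may settle the criteria. It is not available here, and it would not correct the SAP's own tables.

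**Conclusion.** Wrong as written, minor. Table 10 conflicts with Table 9 for haemoglobin below 65 g/L and has no row for 6 of the 17 parameters with scheduled post-baseline values and a grade 3 limit. If Table 10 is used as the grading, which is the plain reading, the grade 3+ listing and the frequency summary need not reconcile.

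It would be tempting to put the gap at 8 of 19 parameters (42%). The documents do not support that as a practical figure, because the two lipids are drawn at Screening only.

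The number of subjects affected cannot be derived from the documents. Glucose and electrolyte values are the more plausible cases: in Protocol Section 5.2.2 diabetes is named as an exclusion only when microalbuminuria is present. No estimate, test or primary result changes. The conclusion rests on the SAP tables alone and uses no outside text of the CTCAE.

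**What to change.** Two edits to SAP Section 11.3.2:

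1. Add one sentence stating that the grade 3+ listing includes every post-baseline value that meets a limit in Table 8 or Table 9. This makes the listing and the frequency summary use one definition and covers all six parameters without new rows in Table 10.
2. In Table 10, remove the 65.0 g/L lower bound from the haemoglobin grade 3 cell, so that grade 3 is below 80.0 g/L and agrees with Table 9.

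The list of tables and listings referred to in SAP Section 17.0 should be checked for the same wording. The cost is SAP text, minor programming and a slightly longer listing. No data collection changes.

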**Table 10. NCI CTCAE Grading**

Test	Grade 1	Grade 2	Grade 3	Grade 4
SGPT/ALT increased	$> \text{ULN} - 3.0 \times \text{ULN}$	$> 3.0 - 5.0 \times \text{ULN}$	$> 5.0 - 20.0 \times \text{ULN}$	$> 20.0 \times \text{ULN}$
SGOT/AST increased	$> \text{ULN} - 3.0 \times \text{ULN}$	$> 3.0 - 5.0 \times \text{ULN}$	$> 5.0 - 20.0 \times \text{ULN}$	$> 20.0 \times \text{ULN}$
GGT increased	$> \text{ULN} - 2.5 \times \text{ULN}$	$> 2.5 - 5.0 \times \text{ULN}$	$> 5.0 - 20.0 \times \text{ULN}$	$> 20.0 \times \text{ULN}$
ALP increased	$> \text{ULN} - 3.0 \times \text{ULN}$	$> 3.0 - 5.0 \times \text{ULN}$	$> 5.0 - 20.0 \times \text{ULN}$	$> 20.0 \times \text{ULN}$
TBL increased	$> \text{ULN} - 1.5 \times \text{ULN}$	$> 1.5 - 3.0 \times \text{ULN}$	$> 3.0 - 10.0 \times \text{ULN}$	$> 10.0 \times \text{ULN}$
Creatinine increased	$> \text{ULN} - 1.5 \times \text{ULN}$	$> 1.5 - 3.0 \times \text{ULN}$	$> 3.0 - 6.0 \times \text{ULN}$	$> 6.0 \times \text{ULN}$
CPK increased	$> \text{ULN} - 2.5 \times \text{ULN}$	$> 2.5 - 5.0 \times \text{ULN}$	$> 5.0 - 10.0 \times \text{ULN}$	$> 10.0 \times \text{ULN}$
Hemoglobin decreased	$< \text{LLN} - 100.0 \text{ g/L}$	$< 100.0 - 80.0 \text{ g/L}$	$< 80.0 - 65.0 \text{ g/L}$	N/A
Neutrophil count decreased	$< \text{LLN} - 1.5 \times 10^9/\text{L}$	$< 1.5 - 1.0 \times 10^9/\text{L}$	$< 1.0 - 0.5 \times 10^9/\text{L}$	$< 0.5 \times 10^9/\text{L}$
WBC decreased	$< \text{LLN} - 3.0 \times 10^9/\text{L}$	$< 3.0 - 2.0 \times 10^9/\text{L}$	$< 2.0 - 1.0 \times 10^9/\text{L}$	$< 1.0 \times 10^9/\text{L}$
Lymphocyte count decreased	$< \text{LLN} - 0.8 \times 10^9/\text{L}$	$< 0.8 - 0.5 \times 10^9/\text{L}$	$< 0.5 - 0.2 \times 10^9/\text{L}$	$< 0.2 \times 10^9/\text{L}$

If there are multiple post-baseline measurements on the same day, the worst value will be used.

### Liver Function Tests

Additional summaries will be presented for liver function tests including ALT or serum glutamic-pyruvic transaminase (SGPT), AST or serum glutamic-oxaloacetic transaminase (SGOT), alkaline phosphatase, and total bilirubin. Each laboratory value will be categorized as follows:

- $< 1.5 \times \text{ULN}$
- $\geq 1.5 \times \text{ULN} - < 3.0 \times \text{ULN}$
- $\geq 3.0 \times \text{ULN} - < 5.0 \times \text{ULN}$
- $\geq 5.0 \times \text{ULN} - < 10.0 \times \text{ULN}$
- $\geq 10.0 \times \text{ULN} - < 20.0 \times \text{ULN}$

---

- $\geq 20.0 \times \text{ULN}$

Shift tables of Baseline to the maximum (relative to the normal range, i.e., the largest multiple relative to the upper limit of normal) values, and from Baseline to final value will be presented using these categories. A listing of potentially clinically important liver function laboratory values will be provided. The listing will include all subjects who met any of the following four criteria:

- $\text{ALT} \geq 3 \times \text{ULN}$ , or
- $\text{AST} \geq 3 \times \text{ULN}$ , or
- Alkaline phosphatase  $\geq 1.5 \times \text{ULN}$ , or
- Total bilirubin  $\geq 2 \times \text{ULN}$ .

A listing of possible Hy's Law cases, defined as those who meet all of the following conditions will be provided:

- $\text{ALT} > 3 \times \text{ULN}$  or  $\text{AST} > 3 \times \text{ULN}$
- Associated with an increase in bilirubin  $\geq 2 \times \text{ULN}$
- Alkaline phosphatase  $< 2 \times \text{ULN}$ .

In addition, a graphical summary highlighting potential cases of Hy's Law within each treatment group will be presented. The maximum on-treatment values of total bilirubin and ALT will be plotted each on a scale as multiples of the upper limit of normal. The figure will show areas that meet the criteria of cholestasis (total bilirubin  $> 2 \times \text{ULN}$ ), Temple's corollary ( $\text{ALT} > 3 \times \text{ULN}$ ) and Hy's Law as the combination of these two factors.

All analyses will be conducted in the Safety Population.

## 11.4 Analysis of Vital Signs and Weight

### 11.4.1 Variables and Criteria Defining Abnormality

The following vital sign parameters will be assessed: Systolic blood pressure [mmHg], Diastolic blood pressure [mmHg], Pulse [beats per minute], Respiratory rate [breaths per minute], Temperature [ $^{\circ}\text{C}$ ], Weight [kg]. The following table presents the Criteria for Potentially Clinically Important Vital Sign Findings.

**Table 11. Criteria for Potentially Clinically Important Vital Sign Findings**

Vital Sign	Category	Criteria for Potential Clinically Important Vital Signs
Systolic Blood Pressure	Low Value	$\leq 90$ mmHg and decrease $\geq 20$ mmHg from Baseline
	High Value	$\geq 160$ mmHg and increase $\geq 20$ mmHg from Baseline
Diastolic Blood Pressure	Low Value	$\leq 50$ mmHg or decrease $\geq 15$ mmHg from Baseline
	High Value	$\geq 105$ mmHg or increase $\geq 15$ mmHg from Baseline
Pulse	Low Value	$\leq 50$ bpm or decrease $\geq 15$ bpm from Baseline
	High Value	$\geq 120$ bpm or increase $\geq 15$ bpm from Baseline
Respiratory rate	High Value	$> 3/\text{min}$ increase from Baseline

### 11.4.2 Statistical Methods

Changes from Baseline to each visit and to the final value in vital sign parameters will be summarized with the mean, standard deviation and median. The Baseline and final value means will also be presented for subjects who have both the Baseline and final values (see Section 6.0 for the definition of Baseline and final values).

For baseline, if there are multiple measurements on the same day, the last measurement prior to the first dose of study drug will be used as the Baseline vital sign value. If there are multiple post-baseline measurements on the same day, average value will be used.

For systolic blood pressure, diastolic blood pressure and pulse, a listing of all subjects with any vital sign value meeting criteria for potentially clinically important values will be provided. For each of these subjects, the whole course of the respective parameter will be

listed. The number and percentage of subjects who have at least one value meeting criteria for potentially clinically important values will be provided for each selected vital sign parameter.

All analyses will be conducted in the Safety Population.

## **11.5                   Analysis of ECG Parameters**

No analyses of ECG will be done.

## **12.0                   Pharmacokinetic Analysis**

Pharmacokinetic analysis is not covered in this SAP.

## **13.0                   Biomarkers Analysis**

Biomarkers Analysis is not covered in this SAP.

## **14.0                   Summary of Changes**

### **14.1                   Summary of Changes Between the Latest Version of Protocol and the Current SAP**

In Section 10.1.2 of this SAP, the strategy for analysis of continuous endpoints was further refined. The protocol had specified ANOVA with treatment group and stratification factor in the model. The SAP now clarifies that for change from baseline in PSS a stratified van Elteren test will be used. For other continuous variables, treatment groups will be compared using ANCOVA with treatment group, Baseline value, and stratification factor in the model. This modification was done to align the study with the other studies in the Risankizumab Psoriasis development program.

In Section 10.3, NAPSI was added as a secondary endpoint to make optimal use of the data collected for NAPPA-CLIN assessments.

---

## 15.0 **Appendix**

### **Appendix A. PASI Calculation**

The PASI score is calculated according to the following formula:

$$\text{PASI} = 0.1(E_h + I_h + D_h)A_h + 0.3(E_t + I_t + D_t)A_t + 0.2(E_u + I_u + D_u)A_u + 0.4(E_l + I_l + D_l)A_l$$

where E, I, D, and A denote erythema, induration, desquamation, and area, respectively, and h, u, t, and l denote head, upper extremities, trunk, and lower extremities, respectively. PASI scores range from 0.0 to 72.0 with the highest score representing complete erythroderma of the severest degree.

### **Appendix B. sPGA Calculation**

The sPGA is a 5 point score ranging from 0 to 4, based on the physician's assessment of the average thickness, erythema, and scaling of all psoriatic lesions.

Erythema, induration and scaling of all psoriatic lesions are scored from 0 – 4. The composite score is the arithmetic mean of erythema, induration and scaling. The final sPGA is determined from this score as follows:

- Clear 0 = 0 for all three
- Almost clear 1 = mean  $> 0, < 1.5$
- Mild 2 = mean  $\geq 1.5, < 2.5$
- Moderate 3 = mean  $\geq 2.5, < 3.5$
- Severe 4 = mean  $\geq 3.5$

### **Appendix C. PPASI Calculation**

The PPASI is a composite score and will be computed for each palm and sole, left and right and is derived from the sum of the scores for erythema (E), induration (I) and desquamation (D) multiplied by the score recorded for the extent of palm and sole area involved. PPASI is calculated as follows: (sum of scored for E + I + D)\*Area \*0.2

(location: right palm) + (sum of scored for E + I + D)\*Area \*0.2 (location: left palm) + (sum of scored for E+I+D)\*Area \*0.3 (location: right sole) + (sum of scores for E+I+D)\*Area \*0.3 (location: left sole). The range is 0 to 72.

#### **Appendix D. PSSI Calculation**

The PSSI is a composite score derived from the sum of the scores for erythema, induration and desquamation multiplied by the score recorded for the extent of scalp area involved. The range is 0 to 72.

#### **Appendix E. NAPPA-CLIN Calculation**

The NAPPA-CLIN is calculated by summing the number of quadrants of the nail affected by a nail matrix psoriasis and number of quadrants of the nail affected by a nail bed psoriasis for the least and the worst affected nail for both hands and/or both feet.

#### **Appendix F. NAPSI Calculation**

The NAPSI score is calculated by summing the scores of all the nails which for each nail are the sum of the nail matrix score and nail bed score. Each of these is scored as 0 = none, 1 = present in 1/4 nail, 2 = present in 2/4 nail, 3 = present in 3/4 nail, 4 = present in 4/4 nail. The NAPSI score is calculated only if all questions in the CRF are completed.

#### **Appendix G. PSS Calculation**

The total PSS score is calculated by summing the score of each question. Each question of the PSS is scored as 0 = none to 4 = very severe. If one or more of the items are missing, the total score will be set to missing.

#### **Appendix H. DLQI Calculation**

The DLQI score is calculated by summing the score of each question. Each question of the DLQI is scored as 0 = not at all, 1 = a little, 2 = a lot, 3 = very much, 0 = not relevant. For question no. 7, yes is scored as 3. If one or more of the items are missing, the total score will be set to missing.

**Appendix I. SF-36 Calculation**

The SF-36 (version 2.0) PCS and MCS scores will be calculated as described in 'SF-36 health survey update. Spine, 2000,' and rounded to 0.1. If one or more of the items are missing, the total score will be set to missing.

**Appendix J. PBI Calculation**

PBI is the arithmetic mean of all rated benefits (PBQ items) weighted by the relative importance of each corresponding need item (PNQ). Each question of PBQ and PNQ is scored as 0 = not at all, 1 = somewhat, 2 = moderately, 3 = quite, 4 = very.

$$PBI = \sum_{i=1}^k \frac{PNQ_i}{\sum_{j=1}^k PNQ_j} PBQ_i$$

If one or more of the items are missing, the total score will be set to missing.

**Appendix K. HADS Calculation**

The HADS considers anxiety and depression. Each question of HADS anxiety and depression is scored as 0 = best to 3 = worst. The scores are summed up to a total score separately for anxiety and depression. If one or more of the four items are missing, the total score will be set to missing. These total scores are categorized as normal (0 – 7), borderline abnormal (8 – 10) and abnormal (11 – 21) for anxiety and depression. If one or more of the items are missing, the total score will be set to missing.

**Appendix L. EQ-5D-5L Calculation**

For calculation of a single index value the German EQ-5D-5L Crosswalk Value Set is used. If one or more of the items are missing, the total score will be set to missing.

